### D. Partial Termination

If the treatment appears at any point to be clearly successful in any patient, the choice of constant stimulation at the best amplitude will be offered. Regardless of whether the stimulation is stopped permanently or left at a constant level, the patient will be followed according to the study plan for as long as they remain willing. The patient may also elect to receive no further stimulation but to stay in the full study to assess pain and other variables.

### E. Futility and Enrichment:

Gradual benefits may be seen from prolonged treatment. Therefore the study will not be stopped early in the absence of interim benefits, nor will the stimulation intensity be increased.

## 13 SELECTION OF PARTICIPANTS

### 13.1 Recruitment Procedure

Some recruitment will be done through the newsletter of the Paralyzed Veterans of America (South Florida Chapter). This is a congressionally chartered Veterans service organization, whose members are veterans of the armed forces who have experienced SCI. In addition, participants will be solicited through the newsletter of the Miami VAMC. Other potential subjects will be identified from a database maintained by The Miami Project to Cure Paralysis. Potential study participants will be asked to contact [name], Chief of the Spinal Cord Injury Service of the Miami VA Medical Center, if they are interested in learning more about the study. [name] will also conduct a medical record review to identify potential participants among the patients who in the past or currently are visiting his clinic. These patients will be contacted by [name] (Study Coordinator) who will inform them about the study over the phone or by sending them a copy of the recruitment material in the mail.

Compensation will be provided for each visit (n=10), as a fixed amount (\$100.00 per visit) to cover expected average travel and incidental costs. An extra payment will be given for participation in the entire study (\$400.00). If a patient does not have a telephone, an inexpensive pay-as-you go cellular telephone will be provided (from additional internal funding sources).

### 13.2 Consent Procedures

Informed consent will be obtained in 3 steps: (1) for clinical and psychological screening, (2) for the main functional testing, (3) for DBS surgery. The Study Coordinator and [name] will address questions during steps 1 and 2 (to be done in the 1st week at the Miami VA Hospital). This will be done in a private examination room, with the patient offered the possibility of reviewing the informed consent form and asking questions for up to 2 weeks before deciding (they would need to make a 2nd visit for this); Drs. [name] and [name] will be present for step 3 (to be done in the 7th week at the University of Miami Hospital). The step 2 consent process will include showing the patient the surgical (step 3) consent form, and explaining the surgery, in order for the potential participants to have 6 weeks to review the surgery consent and ask any question they might have about the procedure. The step 3 consent will explain that the subject may receive the Activa PC+S DBS device system or the Activa PC.

Participants will be screened before the step 2 consent discussion for drug abuse or major psychiatric problems. Literacy is an inclusion criterion. Participants can request a meeting or telephone conversation at any time during the study with the PI or relevant Co-investigator, as well as with the Study Coordinator. The Study Coordinator will be the primary contact for this. Her email address and telephone numbers will be provided to participants for this purpose.

A pregnancy screen will be performed on all females of potential child bearing age. All SCI patients excluded following the screening will be recorded to identify potential factors impeding patient enrollment which can be addressed by the study Executive Committee. Patients unable to provide informed consent will be denied entry into the study. The fully executed informed consents will be placed in the chart, with copies given to the patient and maintained in the site's study binder.

### 13.3 Inclusion Criteria

- a) Age: 22 - 60 years old at last birthday;
- b) Diagnosis of traumatic SCI at or above the 12th thoracic segment (T12) that occurred >365 days;
- c) Neuropathic pain below the level of injury, as determined based on pain in an area with neurological deficit and described as burning, shooting, electric, stinging etc.

- d) The injury must have occurred at least 1 year prior to entering the study and participants must have experienced chronic pain for a minimum of six months.
- e) The disability must have a grade on the American Spinal Injury Association Impairment Scale (AIS) of ASIA-A, ASIA-B, ASIA-C or ASIA-D as determined by qualified examiners.
- f) Pain (neuropathic) of moderate severity or greater is present, when the patient is taking their routine pain medication, with a score of at least 4 on a numerical rating scale (range of 0 to 10).
- g) Participants who are on medications for other conditions, such as diabetes, will be considered as candidates for this study. The dose will be monitored throughout the trial. (They will be excluded if the drug is being used to treat epilepsy, Parkinson's diseases, or other brain degenerative diseases.)
- h) Participants will be allowed to utilize over-the-counter drugs such as NSAIDs, acetaminophen and aspirin. Their use will be documented in the weekly pain assessments. A list of "allowed" medications will be provided to study participants. After the surgery, patients will be allowed to take stay on the protocol if they take Tramadol (50-100 mg, 2 times a day for up to 2 weeks) as a rescue drug in addition to their stable medication.
- i) The patient must be taking pain medication to maintain a stable level of medication from 4 weeks before surgery to 12 weeks after (the primary endpoint), except on the day of surgery. On the day of the surgery, in the presence of a physician who can provide immediate backup pain control if needed, medications will be stopped until the acute effects of DBS on analgesia have been evaluated.
- j) The participant must be willing to comply with the protocol including all scheduled visits.
- k) Autonomic dysreflexia can be present but is not a necessary requirement. Autonomic dysreflexia will be defined as rise of systolic pressure by more than 30 mm Hg during noxious skin stimulation or when the bladder or bowel are full, or apparently spontaneously over a period of minutes
- l) Literate at 8th grade level or above.
- m) Treatment with at least two of the following drug classes must have failed to give satisfactory pain relief within the last two years: anticonvulsants (e.g., pregabalin, gabapentin); antidepressants (e.g., trazodone, amitriptyline); NSAIDs (e.g., ibuprofen). In addition, at least one of the following must have proved ineffective: exercise-based rehabilitation, massage therapy using a variety of methods, acupuncture using pressure, needles, heat, or electrical stimulation on specific points on the body and psychological interventions such as cognitive therapy.
- n) The subject must provide a letter of clearance for the DBS surgery from their primary physician.

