- Beck depression inventory (BDI)
- Guy-Farrar patient global impression of change (PGIC)
- Medication usage

In addition, subjects will be asked to keep a pain diary with a morning and evening pain score rated from 0 (no pain) to 10 (worst ever pain). The pain diary will be retrieved at the visits or by telephone.

At weeks 104 and 156, we will determine the ASIA score (American Spinal Injury Association neurological examination, sensory and motor). On week 156, an open ended qualitative exit interview will be conducted with audiovisual recording, including questions on the overall experience, effects on daily life, etc.

Adverse events (AEs) will be recorded immediately after telephone contact by the subject (subject-reported AEs) and during visits to the study site (clinician-reported AEs).

• **Table 1: List of Procedures for planned study**

Screening:	
1	Urine pregnancy test
2	HIV, HBV, HCV testing
3	Laboratory tests (CBC, CMP, BSCP, prothrombin time test)
4	Medical history, Brief neurological and medical examination
5	Autonomic dysreflexia assessment
6	Spinal Cord Injury history
7	ASIA motor / sensory scores
8	Functional and pain assessments
9	Psychological Assessment (MMSE, BDI)
10	Drug abuse screening test
Baseline Procedures (at 2- weeks):	
1	Autonomic dysreflexia assessment
2	Functional and pain assessments
3	Psychological Assessment (MMSE, BDI)
4	ASIA motor / sensory scores
5	Medical history, Brief neurological and medical examination
6	Patient diary on medications
DBS Device Implantation Surgical Procedure:	
1	Initial MRI / CT scan of the spine
2	Chest X-ray; Electro-cardiogram
3	1-Targeting & Lead placement: at 7-week
3	2-DBS & Lead connection: at 8-week
ICU Monitoring/Medical Treatment:	
1	Blood Pressure Monitoring
2	Oxygenation
3	Additional physiological monitoring specific to subject (displayed on telemetry monitor)
4	Laboratory tests (CBC, CMP, BSCP, prothrombin time test)
5	Post op medications (antibiotics, DVT prophylaxis, etc.)
Follow-Up Procedures:	
1	Long-term DBS in PAG/PVG starting on week 8
2	Telephone interview: weekly, except on-site visit weeks, from week 3
3	Pain assessments: on even weeks, starting on week 10
4	Autonomic Standards Assessments: on on-site visit weeks
5	Tilt table response exam: at 20-week, 32-week, and 52-week
6	Beck Depression Inventory: on visit weeks
7	Folstein Mini-Mental State exam: at 20-week, 32-week, and 52-week

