**Table 2. Flow sheet of Visits/Assessments**

Study Visit Schedule for the initial 52-week study period:

week ( $\pm 7$ days) >>	<<No of tests	1	2	3, 5	4, 6	5, 6	7	8	9, 11, 13, 15, 17, 19	10, 14, 18	12, 16	20, 32	21, 23, 25, 27, 29, 31, 33, 35, 37, 39, 41, 43, 45, 47, 49, 51	22, 26, 28, 30, 34, 36, 38, 42, 44, 46, 50	24, 40, 48	52
SCREENING		x														
SURGERY, or week-5,6 screening for surgery						x	x	x								
LONG-TERM DBS in PAG/PVG (note 1)									x	x	x	x	x	x	x	x
TAPERING or STOPPING of PAIN MEDICATION(S)												x			x	
COMPREHENSIVE TESTING	4		x										x			x
ABBREVIATED TESTING	5										x				x	
TELEPHONIC INTERVIEW	40			x	x				x	x			x	x		
Sites																
Miami VA Medical Center (note 2)		x	x								x	x			x	x
Miami Project in Lois Pope Life Center (note 2)				x	x				x	x	x	x	x	x	x	x
University of Miami Hospital						x	x	x								
Study Therapy																
Targeting and lead placement	1						x									
DBS and lead connection	1							x								
DBS adjustment &-or sensing / possible 5 minute inactivation	9							x			x	x			x	x
General Assessments																
Informed Consent	3	#1	#2				#3									
Spinal Cord Injury history/Demographics	1	x														
Medical history, Brief medical examination	1	x														
Drug Abuse Screening Test (DAST)	1	x														
Folstein Mini-Mental State Examination (MMSE)	4	x											x			x
Beck Depression Inventory (BDI)	9	x									x	x			x	x
(PGIC)	44								x	x	x	x	x	x	x	x
Adverse Event assessment	52		x				x	x	x	x	x	x	x	x	x	x
Vital signs (BP, SpO2, temp)	12	x	x				x	x			x	x			x	x
Patient Diary on Medications	50	x	x	x	x				x	x	x	x	x	x	x	x
Qualitative exit interview	1															x
Neuro System Exams																
ASIA Neurological Exam	4	x											x			x
Tilt table response exam (note 3)	4		x										x			x
Patient Self-assessment of Autonomic Responses	38			x	x				x	x			x	x		
Autonomic Standards Assessment	9		x								x	x			x	x
Multidimensional Pain Inventory (MPI-SCI)	4		x										x			x
Quantitative sensory testing (QST)/Allodynia	4		x										x			x
ISCI Pain Basic Data Set / NPSI	25		x		x					x	x	x		x	x	x
Imaging																
Neuroimaging - MRI study	1						x									
Neuroimaging - CT study	1							x								
Electro-cardiogram (EKG)	1						x									
Chest x-ray	1						x									
Laboratory																
CBC, Comprehensive Metabolic Panel (including Mg + , Renal & Liver Function), PT/PTT	2		x					x								

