### 14.3 Participant Procedures and Assessments

#### 14.3.1 Baseline Assessments

Participants who remain eligible after all the screening procedures are complete will undergo the following baseline assessments at 2- week, prior to surgical procedures.

- Functional Pain Assessments
  - ISCI basic pain dataset and Neuropathic Pain Symptom Inventory (NPSI)
  - West Haven-Yale Multidimensional Pain Inventory for persons with SCI (MPI-SCI)
  - Allodynia testing
  - Quantitative sensory testing (QST)
- Quality of Life assessments
  - Beck Depression Inventory (BDI, version 1a)
- Autonomic Assessment:
  - Autonomic Standards Assessment (BP, HR, sympathetic skin response)
  - Tilt table exam response.

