### **15 SAFETY**

Participants will be continuously monitored throughout a one (1) year evaluation period. Assessments will be performed as outlined in Table 1 and Table 2 in section 13.6. Assessments will also include monitoring of occurrence of AEs (acute, delayed, and/or cumulative), as well for changes in clinical status, neurological status and/or functional status. Safety will be determined as follows:

- a) Adverse events or other safety concerns will be ascribed to one of two categories: (1) general known problems with all types of DBS (e.g. infection) or with untreated SCI (e.g., bladder control failure); (2) problems caused by the PAG/PVG site in particular (e.g., hypotension) or to a specific response of SCI symptoms to DBS (e.g., more pain). The first category will not lead to ejection of the method. The second category can be evaluated more by turning off the stimulation or examining correlations with the 4-week periods of (8-weeks after week 24) adjustment of stimulation amplitudes. Second-category events will be carefully assessed and will lead to discontinuation of the study treatment if they cannot be ascribed to special circumstances in a given patient.
- b) Comprehensive pain, motor and autonomic assessment will occur on screening and enrollment (baseline) and then on on-site visit weeks (weeks 12, 16, 20, 24, 32, 40, 48 and 52).
- c) The correct functioning of the DBS apparatus will be monitored every 4 weeks, after implantation, until week 24. Thereafter this assessment occurs every 8 weeks, and on the last visit (week 52).
- d) Pain Assessments using the ISCI-PDS:B and neuropathic rating scale will evaluate development of neuropathic pain syndromes.

The secondary hypothesis which concerns autonomic assessment will also take place during routine patient visits. Heart rate, blood pressure, sweating, body temperature and breathing will be classified as normal, abnormal, unknown, or unable to access. Within the abnormal category, sub-categories will be

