## 17 STATISTICAL CONSIDERATIONS

### 17.1 Safety Analyses:

The analyses for safety will be mainly descriptive, focusing on trends for within-subject differences and changes in reported pain intensity during routine patient visits for the duration of the study. The expected outcome is stable, long-lasting change in the Pain Assessment Scale score from baseline to 44 weeks post-implant .All AEs and SAEs will be listed and their incidence compared to historical controls. The primary safety analysis will be conducted on all patient data when all 12 participants have completed the study.

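### The dated baseline (week 2) nominally precedes the stable-medication window by 1 to 2 weeks, so change from baseline in pain can include medication changes; the week-4 and week-6 pain scores already scheduled should form the baseline

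*Combined protocol and SAP*

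**What the plan says.** - **Baseline.** Section 14.3.1 states that eligible participants "will undergo the following baseline assessments at 2- week, prior to surgical procedures", and Table 1 gives the same week. Section 15 and the synopsis use the word more loosely: "Comprehensive pain, motor and autonomic assessment will occur on screening and enrollment (baseline". That is no later than week 2.
- **Surgery.** Table 1 has "1-Targeting & Lead placement: at 7-week" and connection of the stimulator in week 8. Section 12.6.1 also puts surgery in weeks 7 and 8.
- **Medication.** Section 13.3 i), repeated in the synopsis, sets the stable period: "The patient must be taking pain medication to maintain a stable level of medication from 4 weeks before surgery to 12 weeks after". Criterion f) asks only for a pain score of at least 4 on routine pain medication; it does not ask for stability at entry.
- **Pain scores.** In Table 2 the row "ISCI Pain Basic Data Set / NPSI" carries a total of 25 and is marked for weeks 2, 4 and 6 before surgery. The medication diary starts in week 1.
- **Analysis.** Section 17.1 expects a "long-lasting change in the Pain Assessment Scale score from baseline to 44 weeks post-implant" and names the NRS pain score as the main dependent variable. Neither 17.1 nor 17.2 says which pre-surgery score or scores form the baseline value.

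**The concern.** Participants act as their own controls, so the long-term pain result is a within-person change from a pre-stimulation value. A stable-medication period is useful when both ends of that change lie inside it. Here the later end does for a comparison at 12 weeks after surgery, but the dated baseline nominally does not. A participant who adjusts medication after week 2 in order to be stable by week 3 or 4 complies fully with the protocol, and any resulting change in pain is then counted together with the effect of stimulation. Calling the analysis descriptive does not help, because a descriptive mean change carries the same shift.

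**Working it through.** **1. Are weeks 4 and 6 really scheduled?** The columns marked in Table 2 for the ISCI/NPSI row are: week 2 (1); weeks 4, 6 (2); weeks 10, 14, 18 (3); weeks 12, 16 (2); weeks 20, 32 (2); the column from 22 to 50 (11); weeks 24, 40, 48 (3); week 52 (1).

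1 + 2 + 3 + 2 + 2 + 11 + 3 + 1 = 25, the stated total. Without weeks 4 and 6 it would be 23. The same reading of the columns reproduces the stated 40 telephone interviews and 44 PGIC assessments.

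**2. Position of the baseline.** Window opens = surgery week − 4; window closes = surgery week + 12.

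| Surgery counted from | Opens | Closes | Gap from week 2 | Pre-surgery pain scores inside |
|---|---|---|---|---|
| week 7 (leads) | week 3 | week 19 | 3 − 2 = 1 week | 4, 6 |
| week 8 (connection) | week 4 | week 20 | 4 − 2 = 2 weeks | 4 (on the boundary), 6 |

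**3. Visit tolerance (7 days either way, Table 2).** If only the week-2 visit moves, the gap is 0 to 2 weeks (surgery week 7) or 1 to 3 weeks (surgery week 8). If surgery moves as well, it is −1 to 3 or 0 to 4 weeks. Some participants could therefore have a baseline inside the window.

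**4. Possible size (illustration; all inputs assumed).** A mean drift m between week 2 and the window passes one-for-one into the mean change. For example, if 3 of 12 participants changed medication and their pain moved by 1 to 2 points, m = 3/12 × 1 to 2 = 0.25 to 0.5 points. The direction is unknown. With n = 12, no stimulation effect and a two-sided 0.05 paired t-test, the chance of an apparent improvement is P(T > 2.201), where T is noncentral t with 11 degrees of freedom and noncentrality m√12/SD:

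| Drift towards improvement | SD 1.5 | SD 2.0 | SD 2.5 |
|---|---|---|---|
| 0 | 2.5% | 2.5% | 2.5% |
| 0.25 | 7.6% | 5.9% | 5.0% |
| 0.5 | 18.3% | 12.2% | 9.2% |
| 1.0 | 55.8% | 35.3% | 24.4% |

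**5. Precision with two baseline scores.** Assume compound symmetry (equal variance σ², equal correlation ρ between all visits). With k baseline scores averaged, Var(change) = σ²[1 + (1 + (k − 1)ρ)/k − 2ρ].

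- k = 1: 2σ²(1 − ρ)
- k = 2: 1.5σ²(1 − ρ)

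The ratio is 0.75 for any ρ: 25% less variance, and a standard error of √0.75 = 0.866 times the single-score value, about 13% smaller. If the week-4 and week-6 scores are more alike than scores further apart, the gain is smaller.

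**6. Reach of the remedy.** 44 weeks after connection is week 8 + 44 = 52, which is 33 or 32 weeks after the window closes (52 − 19 or 52 − 20). The synopsis starts medication reduction in week 20.

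**The case against.** The strongest case against is that this is a small gap in a 12-person, open-label Phase 1 study whose efficacy analysis is descriptive. No passage plans a medication change between week 2 and the window. Participants have had pain for at least six months, at least two drug classes have already failed, and the diary would show any change. All of this stands. It limits the statement to what can happen and does not show that it will.

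A reader might also infer several stronger things that the documents do not support:

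- **That weeks 4 and 6 are excluded from the analysis.** Section 17.1 mentions an initial untreated period, which could include them, and its factor coding is never defined. What can be said is that the only dated baseline is week 2 and that no other is prespecified.
- **That the week-2 score is inflated by regression to the mean, because entry requires a score of at least 4.** Selection inflates the score used for selection. A separate later score is affected only so far as the fluctuation persists. Table 1 lists pain assessments at screening while Table 2 marks no pain instrument in week 1, so the documents do not settle which score selects.
- **That the pre-stimulation score is the only comparator.** Section 12.3 records pain with stimulation off and at rising voltages after implantation, repeated in week 12, and section 12.5 uses periods of inactivation to examine placebo effects. The acute aim does not depend on week 2.
- **That all values up to week 20 are on an unchanged regimen.** Section 13.3 h) permits over-the-counter analgesics and a rescue drug, and the window may close in week 19.

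One objection bears on the remedy. The week-4 and week-6 scores are taken by telephone, whereas weeks 20 and 52 are on site. Of the 22 post-implant ISCI/NPSI scores, 14 are also by telephone, so neither choice of baseline matches the mode throughout. Keeping week 2 as a sensitivity analysis deals with this adequately.

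**Conclusion.** The point holds in a limited form. The dated baseline nominally lies 1 to 2 weeks before the stable-medication window opens, so change from baseline in pain can include medication changes made in between. The gap is short and may vanish for some participants. The size of any bias cannot be derived from the documents; the drift table rests on assumed SDs and on a drift in one direction. The precision gain of 25% in variance rests on compound symmetry.

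The correction is worth making because it is nearly free for pain and puts both ends of the comparison up to 12 weeks after surgery in one nominal medication period. It should not be read as cleaning up the week-52 change. Medication reduction from week 20 is the larger source of mixing there, and no choice of baseline removes it.

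**What to change.** 1. **Pain baseline.** In sections 14.3.1, 17.1 and 17.2, prespecify the baseline for the ISCI NRS and the NPSI as the mean of the week-4 and week-6 scores, using the one available if the other is missing. Repeat the analysis with the week-2 on-site score as a sensitivity analysis. Cost: a sentence in each section and no new data; the downside is a telephone baseline.
2. **Measures with only a week-2 value before surgery** (QST/allodynia, MPI-SCI, tilt table, Autonomic Standards Assessment). From the diary, flag participants whose medication changed between week 2 and the start of their window, by actual dates, and show results with and without them. Cost: one derived variable.
3. **Reconcile sections 13.3 i) and 14.3.1.** State whether the four weeks count from lead placement or from connection, and how the baseline session relates to the stable period. Aligning the week-2-only tests with that period could mean moving a visit or redefining the period, which is for the sponsor to decide.
4. **Reconcile the primary endpoint.** Section 13.3 i) attaches it to 12 weeks after surgery, while the synopsis places the primary endpoint analyses at 44 weeks post-implantation. The re-based comparison is protected only for the former, and the report should say so.

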
Concomitant Medication
	
Concomitant medications and treatments or procedures pertinent to the study treatment or to any adverse events will be recorded including:
 
 
1) name of drug, treatment, or description of procedure,
 
2) start and end dates and times, and
 
3) clinical indication and/or findings.
 
 
Investigational drugs and any other intervention (not part of the guidelines for management of SCI) known to have a potential impact on outcome will be prohibited.
 
Participants will be allowed to utilize over-the-counter drugs such as NSAIDs, acetaminophen and aspirin. Their use will be documented in the weekly pain assessments. A list of “allowed” medications will be provided to study participants. After the surgery, patients will be allowed to stay on the protocol if they take Tramadol (50-100 mg, 2 times a day for up to 2 weeks) as a rescue drug in addition to their stable medication.
 
The patient must be taking pain medication to maintain a stable level of medication from 4 weeks before surgery to 12 weeks after (the primary endpoint), except on the day of surgery. On the day of the surgery, in the presence of a physician who can provide immediate backup pain control if needed, medications will be stopped until the acute effects of DBS on analgesia have been evaluated.
 
On week 20 during a patient visit under medical supervision, patients will be instructed to take one fewer tablet or a smaller dose tablet, wait 4 hours and then see if their pain becomes worse. If it does become worse, they may take medication to reach the original dose. Subsequently, they may follow this procedure at home or during the following visits.

Study Intervention (Device Usage Protocol)
	

Device
	
The study will use PMA authorized, Class III, implantable, Neurostimulation Systems for Deep Brain Stimulation. The Medtronic Activa PC and PC+S DBS device systems will be used as designed without any modifications.

Study Intervention (Device Usage Protocol)	

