#### 13.4 Exclusion Criteria

- a) Any failure to meet above criteria;
- b) Pregnant women or women who are contemplating pregnancy.
- c) Prior history of abusing non-prescribed drugs.
- d) A recent (one-year) history of alcohol abuse.
- e) Renal disease, heart disease or uncontrolled hypertension, liver disease or hepatic cirrhosis.
- f) Active major medical or psychiatric illness; a score of less than 25 on the MMSE.
- g) Significant post-traumatic encephalopathy from head trauma sustained at SCI.
- h) Pain is only nociceptive, due to muscle spasm

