**13.5 Withdrawal Criteria:**

- a) Participants may withdraw consent to participate in this study at any time by informing the Principal Investigator. No further procedures will be performed or information will be collected from participants that withdraw consent. Previously collected data and samples will be used for the study analysis;
- b) The only anticipated circumstance under which the Principal Investigator would terminate a subject's participation is if information was obtained which made the subject ineligible for the study. The primary reason for this premature termination is to be indicated by selecting one of the following definitions:
  - Gradual deterioration in neurological status from incomplete to complete SCI, or change in ASIA grade to a more severe level: B to A, C to A or B, D to A or B or C;
  - Unresolved post-surgical wound infection;
  - Onset of confounding neurological problems such as severe dysesthesia, severe neuropathic pain or changing neurological level;
  - Serious adverse event: discontinuation due to a serious adverse event;
  - Lost to follow-up: the subject fails to return to the study site for scheduled visits and does not respond to attempts to contact;
  - Withdrew consent: the subject decides to stop his participation for any other reason than an adverse event, or is unable to complete the study as described in the study protocol;
  - Administrative: the Sponsor decides to terminate an individual subject or decides to discontinue the study due to general safety concerns;
  - Protocol violation: anything that is a direct and significant violation of the clinical study protocol.

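### Stable pain medication to 12 weeks after surgery is written as an inclusion criterion, which leaves open an outcome-related route for ending an implanted participant's follow-up

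*Combined protocol and SAP*

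**What the plan says.** **The criterion.** Section 13.3 i): "The patient must be taking pain medication to maintain a stable level of medication from 4 weeks before surgery to 12 weeks after". The same item labels the 12-week point as the primary endpoint and makes an exception for the day of surgery.

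**What follows from failing it.** The first exclusion criterion, 13.4 a), reads "Any failure to meet above criteria". Section 13.5 b) gives one circumstance in which the investigator is expected to end participation, namely that "information was obtained which made the subject ineligible for the study". The reasons listed below it include "Protocol violation: anything that is a direct and significant violation of the clinical study protocol". The parallel list in 12.7 C is permissive: the investigator may remove a subject.

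**What extra analgesia is allowed.** Section 13.3 h) permits over-the-counter analgesics, and a rescue drug for a limited time after surgery on top of stable medication. The synopsis introduces the rescue allowance with "patients will be allowed to stay on the protocol if they take Tramadol".

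**Where the synopsis puts the rule.** The stability sentence stands under Concomitant Medication and is absent from the synopsis list of major inclusion criteria.

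**Analysis.** Section 17.1 makes the 0-10 NRS pain score the main dependent variable. Section 17.2 plans a descriptive efficacy analysis of all twelve enrolled participants from baseline to week 52. Section 17.4 plans regression imputation and names no model or predictors.

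**The concern.** An eligibility criterion should be decidable when the participant enters. Half of this one is decided only in the 12 weeks after a brain implant, by a quantity closely tied to the trial's main outcome. Participants whose pain is poorly controlled tend to take more analgesia, and those with good relief may take less. If a change in medication is handled as a failed criterion, staying in the study depends on the pain result.

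Two things are at stake. The first is the pain estimate: there are 12 participants and no control group, so one lost participant is 8% of the data (1/12). The second is the scheduled follow-up of people carrying an implanted device, when Aim 1 in 11.1 concerns adverse effects over up to 40 weeks. Section 15 b) schedules on-site visits at weeks 12, 16, 20, 24, 32, 40, 48 and 52. A participant removed just after week 12 would miss seven of those eight.

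**Working it through.** The plan states no SD, effect size or power for pain, so there is no figure to reproduce. The check is a reading of the text, followed by an illustration of size.

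**1. When the criterion can be judged.** Section 12.6.1 places surgery in study weeks 7 and 8. Twelve weeks later is study week 19 to 20 (7 + 12, 8 + 12). The post-surgery half is therefore undecided at consent, at baseline and at implantation.

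**2. The route to removal.** A participant whose medication changes in that window does not meet 13.3 i). Under 13.4 a), failing any inclusion criterion is an exclusion. Under 13.5 b), information that makes a subject ineligible is the ground for termination. A second route is to class the change as a protocol violation. Neither 12.7 C nor 13.5 b) lists a medication change by name, and 12.7 C is permissive. Use within 13.3 h) is allowed, so only changes beyond it are exposed.

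**3. What happens afterwards.** Section 13.5 a) stops data collection for those who withdraw consent and keeps their earlier data. Section 13.5 b) does not say whether assessments continue when the investigator ends participation. No section says how pain scores recorded under added analgesia are treated.

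**4. Possible size.** Assumptions: 12 participants, normally distributed pain change, no true effect, the k participants with the worst change are lost and not recovered, k = 1 to 3, SD of change 1.5 to 2.5 NRS points. The expected three largest of 12 standard normal values are 1.629, 1.116 and 0.793. The full set has mean zero, so the shift in the mean of those remaining is

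shift = (sum of the k largest) / (12 − k), toward benefit.

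| k | Calculation | Shift (SD) | NRS points at SD 1.5 / 2.0 / 2.5 | If removal correlates 0.5 with pain change |
|---|---|---|---|---|
| 1 | 1.629 / 11 | 0.148 | 0.22 / 0.30 / 0.37 | 0.11 / 0.15 / 0.19 |
| 2 | 2.745 / 10 | 0.274 | 0.41 / 0.55 / 0.69 | 0.21 / 0.27 / 0.34 |
| 3 | 3.538 / 9 | 0.393 | 0.59 / 0.79 / 0.98 | 0.29 / 0.39 / 0.49 |

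The last column is half the one before it, because the expected pain change given the removal variable is scaled by the correlation. A simulation of 100,000 trials agrees to within 0.01 points.

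**5. Offset.** If one participant with the best relief is also lost for reducing medication, then with the two worst gone the shift is (1.629 + 1.116 − 1.629) / 9 = 0.124 SD instead of 0.274. One from each end gives zero.

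**6. Which time point.** Section 13.3 i) and the synopsis medication row call 12 weeks the primary endpoint. The synopsis safety-analysis row puts the primary endpoint analyses at 44 weeks after implantation. From week 8 these are study weeks 20 and 52.

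**The case against.** The strongest reply is that this is a conduct rule in the wrong list and that nobody would apply it mechanically. Section 13.3 also contains items that no one can fail: h) is a permission, and k) says a condition need not be present. The synopsis already treats the sentence as a medication rule. Section 19.4 already requires important deviations on eligibility and patient management to be documented and summarised. All of this stands, and it is why the point concerns wording that permits removal, not a stated intention to remove. It does not close the route, because 13.4 a) makes no exception for item i). The synopsis list covers only major criteria, so its omission of the rule does not overrule 13.3.

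Four stronger readings are tempting, and the documents do not support them.

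- *Anyone who needs more analgesia is removed.* Section 13.3 h) allows over-the-counter drugs and time-limited rescue, and removal is discretionary.
- *Non-responders leave the data, so the result is biased toward benefit.* No section says that data are dropped; 17.2 includes everyone enrolled and 17.4 imputes. The protection is partial: scores never collected can only be imputed, the model is unstated, and imputing from earlier scores need not recover values missing because pain later worsened. The bias is likely in direction but not established.
- *Safety follow-up is lost.* Appendix 1, item 3.1, ties adverse event reporting to 30 days after the last voltage output, not to continued enrolment, and item 4 covers post-study device-related events. Only the scheduled assessments are in doubt.
- *Section 12.7 D contradicts the criterion.* It says "Regardless of whether the stimulation is stopped permanently or left at a constant level, the patient will be followed according to the study plan", but it concerns clearly successful treatment or stopping stimulation, not medication.

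**Conclusion.** The point holds as a defect of wording with a plausible effect on the results. A condition knowable only after implantation is written as eligibility, and 13.4 a) and 13.5 b) turn it into permission to end participation for a reason related to pain. The synopsis and 13.3 do not agree on what kind of rule it is.

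If the worst 1 to 3 of 12 were lost and not recovered, the mean change would move by about 0.15 to 0.39 SD toward benefit, or 0.2 to 1.0 NRS points at an assumed SD of 1.5 to 2.5. With a correlation of 0.5 this halves to about 0.07 to 0.20 SD. These figures show direction and rough size only. They rest on an assumed SD, an assumed number removed and no useful recovery by imputation, and removing participants who reduced medication would shrink them.

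**What to change.** 1. Limit the eligibility wording of 13.3 i) to the period before surgery, which can be verified.
2. Place the post-surgery stability sentence with the concomitant-medication rules, as the synopsis does, and record breaches as deviations under 19.4. Reconcile 13.3, 13.4 a), 13.5 b) and the synopsis accordingly.
3. State that a medication change does not by itself end the scheduled safety and pain assessments of an implanted participant.
4. Analyse all recorded pain scores. Pre-state a sensitivity analysis for scores recorded under analgesia beyond the permitted level, for example setting them to the pre-implant value. This is needed because added analgesia can itself favour benefit, so retention alone is not a full remedy.
5. Reconcile the 12-week and 44-week primary time points.

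No change to any drug, dose or rescue rule is proposed. The cost is relocated wording, one extra analysis, and possibly a less favourable pain result.
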